14.1.2. Sample Size/Accrual Rate

The number of patients accrued to the study will depend on the MTD. No more than 18 evaluable patients will be treated in the phase I portion. An evaluable patient is defined as one who either a) receives at least one dose the study drug and/or suffers DLT, or b) completes a treatment cycle and has no DLT observed during this cycle.

14.2. Phase II Portion of the Study

The study primary endpoint will be analyzed once the last patient on treatment is on study for 18 weeks.

14.2.1. Study Populations:

Safety population: patients who received any amount of the study regimen.

[figure not shown]
Efficacy population: patients who received at least one cycle of the treatment and at least one efficacy evaluation.

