5.3 Diagnostic Plan

Patients will be evaluated for safety and efficacy at regular intervals. Initial visits will begin 2 weeks after starting duvelisib to evaluate labs and for drug tolerance and will continue on 2 week intervals for 4 cycles. After this time if minimal/no toxicity is noted, visits may be spaced to every 4 weeks. Additional visits are permissible at the discretion of the treating physician. For example, additional visits for monitoring an AE or for concerns of clinical deterioration may be performed. Additionally, imaging for efficacy analyses will be performed at 12-week intervals. The first imaging evaluation may be performed before 12 weeks if there is clinical concern for deterioration or progression.

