7.7 Method of Subject Assignment to Treatment Groups

The study is a single arm, non-randomized trial. Patients will first be allocated to Phase I dose escalation cohorts at each dose level listed in Table 7.5. Patients will be enrolled and allotted to the next available opening for each dose cohort as specified. For the Phase II dose expansion cohort, all patients will be enrolled at the recommended phase II dose.

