12.0 Assessment of Disease

Patients will be evaluated for response every 12 weeks while on study. If clinicians have clinical concerns, evaluation by imaging may be done as there is clinical or subjective evidence of progression before 12 weeks, with imaging resumed on a Q 12-week imaging cycle. Assessments for response and progression will be carried out according to the Response Evaluation Criteria in Solid Tumors (RECIST) guideline version 1.1¹⁹ which are reproduced and paraphrased in the sections below. Following RECIST criteria, changes in the largest diameter of the tumor lesions and the shortest diameter for malignant lymph nodes will be used.

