12.3.3 Evaluation of best overall response

The best overall response is the best response recorded from the start of the treatment until disease progression/recurrence. The reference for progressive disease is the smallest measurement since treatment initiation. The best response assignment will depend on the achievement of both measurement and confirmation criteria, as seen in the tables below, excerpted from the RECIST v1.1 manuscript ¹⁹.

For patients with measurable disease

Target Lesions	Non-Target Lesions	New Lesions	Overall Response	Best Overall Response when Confirmation is Required*
CR	CR	No	CR	≥4 wks. Confirmation**

CR	Non-CR/Non-PD	No	PR	≥ 4 wks. Confirmation**
CR	Not evaluated	No	PR	
PR	Non-CR/Non-PD/not evaluated	No	PR	
SD	Non-CR/Non-PD/not evaluated	No	SD	Documented at least once ≥ 4 wks. from baseline**
PD	Any	Yes or No	PD	no prior SD, PR or CR
Any	PD***	Yes or No	PD	
Any	Any	Yes	PD	

* See RECIST 1.1 manuscript for further details on what is evidence of a new lesion.
** Only for non-randomized trials with response as primary endpoint.
*** In exceptional circumstances, unequivocal progression in non-target lesions may be accepted as disease progression.

Note: Patients with a global deterioration of health status requiring discontinuation of treatment without objective evidence of disease progression at that time should be reported as "*symptomatic deterioration*." Every effort should be made to document objective progression even after discontinuation of treatment.

For patients with non-measurable disease (i.e. non-target disease)

Non-Target Lesions	New Lesions	Overall Response
CR	No	CR
Non-CR/non-PD	No	Non-CR/non-PD*
Not all evaluated	No	not evaluated
Unequivocal PD	Yes or No	PD
Any	Yes	PD

* 'Non-CR/non-PD' is preferred over 'stable disease' for non-target disease, since SD is increasingly used as an endpoint for assessment of efficacy in some trials, so to assign this category when no lesions can be measured is not advised

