14.2.3. Analysis of Primary and Secondary Endpoints

14.2.3.1. Analysis of Tumor Response:

Overall Response Rate (**primary endpoint**) will be estimated by the proportion of patients with a best response of complete response (CR) or partial response (PR) by RECIST 1.1 criteria, with corresponding exact 95% confidence limits being reported. The response rate will also be compared between pre-

specified subsets of melanoma patients with Fisher's exact tests. These comparisons will be done in an exploratory manner.

The distribution of response duration (defined in Section 12.3.4) will be characterized by median and quartiles, with the corresponding Kaplan-Meier estimate being made of PFS among patients responding to treatment. To the extent possible from the available data, proportional hazards models will be used to assess whether the rate of disease progression varies materially among the three subgroups of disease response: CR, PR, and SD.

14.2.3.2. Analysis of Progression Free Survival (PFS) and Overall Survival (OS):

PFS and OS (defined in Section 12.3.5 and 12.3.6 respectively) will be estimated by the Kaplan-Meier method. The corresponding median survival times (with 95% confidence limits) will be determined, as will the cumulative percentage of patients remaining progression-free (and the cumulative percentage-alive) at selected time points after initial treatment (e.g., 6,12, 18 months).

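### The 18-week primary analysis comes 5 to 7 weeks before the first scheduled scan that can confirm a week-12 response in the last patients enrolled

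*Combined protocol and SAP*

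**What the plan says.** Section 14.2 fixes the analysis date: "The study primary endpoint will be analyzed once the last patient on treatment is on study for 18 weeks".

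Section 14.2.3.1 defines the primary overall response rate as the "proportion of patients with a best response of complete response (CR) or partial response (PR) by RECIST 1.1 criteria". It neither requires nor waives confirmation, and it does not point to the section that defines best response.

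That definition is in Section 12.3.3: "The best response assignment will depend on the achievement of both measurement and confirmation criteria". The table there lists confirmation at 4 weeks or later for CR and PR, with a footnote limiting the requirement: "Only for non-randomized trials with response as primary endpoint". Section 7.7 places this trial in that class: "The study is a single arm, non-randomized trial".

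On imaging, Section 12.0 says "Patients will be evaluated for response every 12 weeks while on study", and Section 5.3 says "imaging for efficacy analyses will be performed at 12-week intervals". Section 3.2.1 gives the same interval, and Table 6.7.1 adds a window of 7 days either side. Section 12.0 ties unscheduled imaging to "clinical or subjective evidence of progression before 12 weeks, with imaging resumed on a Q 12-week imaging cycle". The Protocol Summary also allows extra imaging for toxicity or clinical concern. No section calls for a scan to confirm a response.

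**The concern.** These provisions cannot all be followed for the last patients enrolled. The endpoint needs a second scan at least 4 weeks after the first response, the schedule puts that scan near week 24, and the analysis is dated to week 18.

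Success needs more than 3 responses in 30 patients (Section 14.2.2), so one unconfirmed response can decide the trial. Section 14.2 does not say whether a response still awaiting confirmation counts, fails or waits. If it fails, late entrants are held to a test that they had no scheduled chance to pass. The main risk is wrongly discarding an active combination, with power below the figure of more than 86% that the plan states.

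**Working it through.** **1. Timing.** The inputs are a first scan at week 12, a 12-week interval, a window of 1 week either side (Sections 3.2.1 and 5.3, Table 6.7.1), a minimum of 4 weeks to confirmation (12.3.3) and the analysis at week 18 (14.2). The clock is assumed to start at first dose.

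- Scan 1: weeks 11 to 13. Scan 2: weeks 23 to 25.
- Gap from analysis to scan 2: 23 − 18 = 5 weeks to 25 − 18 = 7 weeks.
- Earliest date that meets the 4-week rule: 11 + 4 = 15 to 13 + 4 = 17 weeks. This is before week 18, but no scan is scheduled then.

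If time on study ran instead from consent, up to 28 days before treatment (Section 3.1.2), the gap would be 5 to 11 weeks.

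**2. The plan's own figures.** Section 14.2.2 stops for futility at 0 responses in the first 15 and declares success at 4 or more in 30. By exact binomial,

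P(success) = P(at least 1 response in the first 15, and at least 4 in total).

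- True rate 20%: 0.8649 (plan: over 86%).
- True rate 5%: 0.0582 (plan: below 0.06).
- Early stop: 0.95^15 = 0.463 at 5% (plan: above 0.46), and 0.80^15 = 0.0352 at 20%. The plan says less than 3.5% for the latter, a rounding or simulation difference.

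The stated design is reproduced.

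**3. How many patients are affected.** With even spacing, k = floor(gap / spacing) + 1. Section 14.0 gives 1 to 2 patients per month per centre, and Section 5.1 now names one site. The 42 patients in 18 months imply 42/18 = 2.33 per month.

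| Accrual per month | Spacing (weeks) | k for a gap of 5 to 7 weeks |
|---|---|---|
| 1 | 4.35 | 2 |
| 2 | 2.17 | 3–4 |
| 2.33 | 1.86 | 3–4 |

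**4. Effect if those k patients cannot contribute.** The rule is unchanged, with only 30 − k patients able to count.

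| k | Power at 20% | Type I error at 5% |
|---|---|---|
| 0 | 0.865 | 0.058 |
| 2 | 0.831 | 0.048 |
| 3 | 0.811 | 0.043 |
| 4 | 0.788 | 0.038 |

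The last patient alone (k = 1) already brings power to 0.849.

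**5. Sensitivity.** The documents do not say how many week-12 responses are lost before week 24, so the shares below are assumptions. A share f lost lowers the confirmable rate to 0.20 × (1 − f).

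| Share lost | Power at 18 weeks (k = 2 to 4) | Power at 25 weeks | Recovered by the later date |
|---|---|---|---|
| 0% | 0.831–0.788 | 0.865 | 0.03–0.08 |
| 10% | 0.758–0.708 | 0.800 | 0.04–0.09 |
| 20% | 0.666–0.610 | 0.714 | 0.05–0.10 |

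If none are lost but 10% to 20% of responses first appear at week 24, power with a 25-week analysis is 0.860 to 0.841, because the latest entrants' week-24 responses are still unconfirmed.

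**The case against.** The strongest objection is that Section 14.2 gives an analysis date and does not say that pending responses fail. Best response under 12.3.3 runs until progression, scanning continues, and Section 4.4.1 expects 3 years of data collection for response duration. If the team waits for later scans, the date does no harm. This stands: the power loss is conditional. But the plan does not say that it will wait, and the handling should be settled before the data are seen.

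Second, the sponsor may have meant an unconfirmed response rate. The endpoint definition and the analysis section never use the word confirmed, and the 12.3.3 table is excerpted from the RECIST paper. On that reading 18 weeks is enough. However, the text of 12.3.3 says otherwise for this type of trial, and nothing waives it. If unconfirmed response was intended, 12.3.3 and 14.2.3.1 still have to be reconciled.

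Third, weeks 15 to 17 fall before week 18, so the flaw may be a missing confirmation scan and not a wrong date. That is a fair inference, and such a scan is a valid alternative. It would also keep responses that fade before week 24, which the later date does not.

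Fourth, only patients who respond are affected. At a 20% rate, the chance that none of 2 to 4 late patients responds is 0.8^2 = 0.64 to 0.8^4 = 0.41. The power figures already average over this. A response seen on an early unscheduled scan, by about week 8, could also be confirmed at week 12, but that scan is meant for suspected deterioration or progression.

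The accrual rates are assumptions too. The two-centre upper rate of 4 per month would give k = 5 to 7 and power as low as 0.70, so this point enlarges the problem.

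**Conclusion.** The concern holds. As written, a week-12 response in the last entrants cannot be confirmed on a scheduled scan by the primary analysis, which falls 5 to 7 weeks too early. The timing gap follows from the documents, taking first dose as the start of the clock.

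The loss of power, 0.03 to 0.08 from a base of 0.865, depends on further assumptions: the result is taken at 18 weeks, pending responses count as non-responses, accrual is evenly spaced at 1 to 2.33 per month, and no responses are lost before week 24 or first seen then. The direction is conservative. The change should be made: it affects which responses count toward the primary endpoint, but the effect is limited to a few patients and disappears if pending responses are resolved first.

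**What to change.** In Section 14.2, set the primary analysis for when the last patient has completed the week-24 scan window (25 weeks from first dose) or has earlier progressed, died or withdrawn. In Section 14.2.3.1, state that the overall response rate is confirmed CR plus PR as defined in 12.3.3.

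This gives late entrants the scheduled confirming scan that earlier entrants already have. It does not ensure that every response is confirmed. Responses lost before week 24 still fail, as they do for everyone else. Responses first seen at week 24 in the latest entrants remain unconfirmed and should be reported as such.

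The cost is about 25 − 18 = 7 weeks' delay and a few sentences, with no added procedure.

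The alternative is a confirmation-scan line in Table 6.7.1 at 4 weeks or more after first response (weeks 15 to 17 for a week-12 response). It keeps the 18-week date and the responses that fade between then and week 24, at the cost of one extra scan per responder, about 0.20 × 30 = 6 patients at a 20% rate.

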12.3 Response Criteria

12.3.1 Evaluation of target lesions

- Complete response (CR) – Disappearance of all target lesions. Any pathological lymph nodes (whether target or non-target) must have reduction in short axis to <10 mm.

- Partial response (PR) – At least a 30% decrease in the sum of diameters of target lesions, taking as reference the baseline sum diameters.
- Progressive disease (PD) – At least a 20% increase in the sum of diameters of target lesions, taking as reference the smallest sum on study (this includes the baseline sum if that is the smallest on study). In addition to the relative increase of 20%, the sum must also demonstrate an absolute increase of at least 5 mm. (Note: the appearance of one or more new lesions is also considered progression).

Patients with a global deterioration of health status requiring discontinuation of treatment without objective evidence of disease progression at that time should be reported as “symptomatic deterioration.” Every effort should be made to document the objective progression even after discontinuation of treatment.

- Stable disease (SD) - Neither sufficient shrinkage to qualify for PR nor sufficient increase to qualify for PD, taking as reference the smallest sum diameters while on study.

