14.2.2. Study Design and Interim Analysis

The primary objective of this study is to evaluate the overall response rate to the combination of anti-PD1 therapy and duvelisib. We would consider the combination futile and not worth further study if the response rate is 5% or lower. We will monitor the efficacy of the regimen using a Bayesian method. We will consider the trial futile and propose stopping if the posterior probability that response rate is <5% given the observed data is >70%. A non-informative prior of Beta (0.5, 0.5) is used for the true response rate and the cohort size is set to be 5. The futility early stopping boundaries are given in the following table:

# Patients (inclusive)	# Responses (inclusive) are considered futile	Actions
5	Never stop with this many patients	
10	Never stop with this many patients	
15	0	Early stopping
20	0	Early stopping
25	0	Early stopping

Therefore, if none of the first 15 patients responds to the combination, the study will be stopped early for futility. Otherwise, the study will continue to recruit all 30 patients. By the end of the study, we will consider the study combination effective and worth further study if the posterior probability that the response rate is $>5\%$ given the observed data is 90% or higher (in our case, if we observe >3 responses in 30 evaluable patients). The following figure demonstrated the simulation results of the operating characteristics of our study design, under the assumption of various true response rates. As shown, when the response rate is 5% or lower, the probability of early stop is higher (>0.46) and probability of declaring efficacy (i.e. “type I error”) is low (<0.06). When the response rate is 20% or higher, the probability of early stopping is less than 3.5% and the probability of declaring efficacy (i.e. “power”) is over 86%.

The simulation is performed using the web tool for Bayesian Efficacy Monitoring Via Posterior Probability (<http://www.trialdesign.org/one-page-shell.html#BEMPO>).

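### The primary response rate is not explicitly assigned to an analysis set, and the natural candidate (14.2.1) excludes treated patients who stop before any efficacy evaluation

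*Combined protocol and SAP*

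**What the plan says.** All references are to the combined protocol and SAP.

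- **14.2.3.1** says the primary ORR "will be estimated by the proportion of patients with a best response of complete response (CR) or partial response (PR"), with exact 95% limits. It names no analysis set.
- **14.2.1** defines two phase II sets. The safety set is everyone who received any of the regimen. The other reads: "Efficacy population: patients who received at least one cycle of the treatment and at least one efficacy evaluation". Neither is linked to the ORR.
- **14.2.2** refers to the count in three ways. The futility rule says "if none of the first 15 patients responds to the combination, the study will be stopped early for futility". For a trial that passes the futility looks, the wording is that "the study will continue to recruit all 30 patients". Success is a posterior probability of at least 90% that the ORR exceeds 5%, given as more than 3 "responses in 30 evaluable patients". The word evaluable is not tied to a definition.
- **12.1** calls a patient evaluable for objective response after re-evaluation at 12 weeks, or if objective progression occurs before the end of cycle 1.
- **12.3.1** covers patients with "global deterioration of health status requiring discontinuation of treatment without objective evidence of disease progression". They are reported as symptomatic deterioration, with no response category. The best-response table in **12.3.3** has no row for a patient with no assessment after baseline.
- **14.0** sets a phase II total of 30, six of them carried over from phase I. There is no phase II replacement rule.

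**The concern.** The first scheduled response assessment is at 12 weeks (5.3 and 12.0). A treated patient who dies, deteriorates or stops for toxicity before any evaluation is very unlikely to be a responder. Leaving that patient out shrinks the denominator and leaves the numerator alone, so the ORR rises because the regimen failed early in some patients.

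The two definitions of evaluability also disagree. Progression before the end of cycle 1 counts under 12.1, but drops out of 14.2.1 if receiving a cycle means completing it. Progression on an early scan between weeks 4 and 12 is inside 14.2.1 but not covered by 12.1; that difference causes no upward bias under 14.2.1.

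Three things are at stake: the ORR estimate, the futility looks, and whether a borderline result is called a success. The study is open label, so an unstated denominator could be settled with the responses in view.

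**Working it through.** **Inputs from 14.2.2 and 14.0.** Beta(0.5, 0.5) prior; stop for futility at 0 responses in 15, 20 or 25; success at 4 or more of 30; null 5%, target 20%; phase II total 30.

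**Step 1: reproduce the plan.** A trial with a response among the first 15 cannot have none at 20 or 25, so P(early stop) = (1 − p)^15.
- p = 0.05: 0.95^15 = 0.463 (stated above 0.46).
- p = 0.20: 0.80^15 = 0.0352 (stated below 3.5%; within simulation rounding).

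P(success) = P(at least 1 response in the first 15 and at least 4 in 30), exact binomial: 0.058 at 5% (stated below 0.06) and 0.865 at 20% (stated over 86%). Posterior Pr(ORR > 5%) is 0.890 at 3/30 and 0.968 at 4/30, which gives the cut-off of more than 3. The plan's figures reproduce.

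**Step 2: effect on the estimate.** The documents give no excluded share, so let u = 5, 10, 15 or 20% of treated patients be excluded, all non-responders (assumption). The rate among those left is p/(1 − u). For example, 0.20/0.90 = 22.2%. With six responders: 6/30 = 20.0% (exact 95% CI 7.7–38.6), 6/27 = 22.2% (8.6–42.3), 6/24 = 25.0% (9.8–46.7).

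**Step 3: effect on the futility look.** If the first 15 means the first 15 evaluable, P(early stop) at a true 5% of all treated is (1 − 0.05/(1 − u))^15.

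**Step 4: effect on the go decision, under three readings.**
- A: 30 treated, no replacement, cut-off fixed at more than 3. Evaluable n is binomial(30, 1 − u).
- B: accrual continues to 30 evaluable, and the 5% null refers to all treated patients.
- C: as A, but the 90% posterior rule is re-applied at the evaluable n. Three responses fail at n = 29 (0.899) and pass at n = 28 (0.908), so the bar drops from 4 to 3.

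| u | True 20% reported as | Early stop at 5% | A: type I | A: power | B: type I | C: type I |
|---|---|---|---|---|---|---|
| 5% | 21.1% | 0.444 | 0.059 | 0.868 | 0.068 | 0.108 |
| 10% | 22.2% | 0.424 | 0.059 | 0.871 | 0.079 | 0.153 |
| 15% | 23.5% | 0.403 | 0.060 | 0.873 | 0.093 | 0.172 |
| 20% | 25.0% | 0.380 | 0.060 | 0.875 | 0.110 | 0.180 |

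Under B, if the 5% null refers to evaluable patients, type I error stays at 0.058. B also needs on average 30/(1 − u) = 31.6 to 37.5 treated patients, more than the 30 in 14.0. Under C, 0.095/0.121/0.122/0.111 would arise from the lower bar alone, with a true 5% among evaluable patients. The denominator adds the remaining 0.012/0.031/0.051/0.068.

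**The case against.** **The label points to an answer.** The set in 14.2.1 is called the efficacy population, the ORR is the primary efficacy endpoint, and 14.2.2 speaks of evaluable patients. A reader might infer that the plan offers no denominator at all. That goes too far: the text points to an evaluable set without assigning it. But accepting that reading confirms the bias, and 12.1 still disagrees.

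**An unbiased reading exists.** Taken literally, a patient with no recorded response has no best response of CR or PR and stays in the denominator of 14.2.3.1 as a non-responder. This stands, so the bias is conditional. Nothing in the text chooses this reading over the other.

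**Losses are limited.** Earlier imaging is allowed on clinical concern. Section 12.3.1 asks for every effort to document progression after treatment stops, and caliper-measured lesions count as evaluations. In 12.3.3, new lesions or non-target progression give PD whatever the target status. This narrows the gap to patients with no evaluation at all, but still does not classify them.

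**A third definition is not a rival.** A reader might add 14.1.2, "An evaluable patient is defined as one who either a) receives at least one dose the study drug and/or suffers DLT", as a competing definition. It sits under phase I and concerns evaluability for dose-limiting toxicity, so it is not a real candidate for the phase II ORR.

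**The shift is modest.** A move from 20% to at most 25% is small beside an interval of 7.7–38.6%. That is fair on precision, but the bias is systematic and avoidable.

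**Conclusion.** The point holds and should be fixed. The primary ORR is not explicitly assigned to a set. The natural candidate conditions on reaching an efficacy evaluation, and no text counts treated patients without one as non-responders. If the 14.2.1 set is used, a true 20% is reported as 21.1–25.0%, and early stopping at a true 5% falls from 0.463 to 0.444–0.380. Both ranges assume that 5–20% of treated patients are excluded and that none responds.

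A reader might infer that the stated type I error and power are wrong. The documents do not support that in general. With 30 treated and a fixed cut-off of more than 3, they stay essentially within the stated limits (0.059–0.060 and 0.868–0.875). Type I error rises to 0.068–0.110 with accrual to 30 evaluable, and only if the 5% null refers to all treated patients. It rises further if the posterior rule is re-applied at a smaller n. Section 14.2.2 states the 90% posterior as the criterion and the cut-off as its instance at 30, and does not say what happens at another n. That the figures hold on some readings and fail on others is the reason to fix the denominator in advance.

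**What to change.** - In 14.2.3.1 and 14.2.2, name all phase II patients treated at the recommended phase II dose as the single denominator for the ORR, the futility looks and the success rule. Measurable disease is already an entry criterion (4.1).
- Count patients with no post-baseline assessment, including symptomatic deterioration without one, as non-responders, and state that they are not replaced.
- In 14.2.2, change 30 evaluable to 30 treated, and keep more than 3 of 30 as the governing rule.
- Include every phase I patient treated at that dose, whether or not the 75%-of-pills rule (12.1, 14.1.1) was met. Otherwise the carry-over is selected on compliance. If more than six carry over, reduce new enrolment so that the total stays 30.
- Keep the 14.2.1 set as a sensitivity analysis and reconcile 12.1 with it.
- State whether the 20% target refers to treated or evaluable patients.

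**Cost.** Only wording in 12.1 and 14.2.1–14.2.3; no new data. The reported ORR is slightly lower. If the target was meant for treated patients, power stays 0.865. If it was meant for evaluable patients, the rate among 30 treated is 0.20(1 − u). Power must then be restated as 0.835/0.800/0.760/0.714 at 5/10/15/20% unevaluable, and early stopping at the target rises from 0.035 to 0.042/0.051/0.061/0.073.
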